5.3 THE ASSOCIATIONS BETWEEN THE INTERVENTION ARMS AND CLINICAL OUTCOMES

5.3.1 The onset of sensory and motor block

From table 5.4, there are no significant differences between the two intervention arms with respect to the sensory and motor block onsets. These are corroborated by the small median differences in both clinical outcomes when comparisons are made between these two groups.

5.3.2 The degrees of sensory and motor block

Based on inspection of table 5.5, there are no significant differences with regard to the degrees of sensory and motor block at 30 minutes following supraclavicular BPB between the two intervention arms (p values of 1 for both outcome parameters). The odds ratio cannot even be computed because there are cells with 0 count.

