THE EFFICACY OF PARECOXIB 20MG AS AN ADJUNCT IN 0.75% ROPIVACAINE IN SUPRACLAVICULAR BRACHIAL PLEUXS BLOCK FOR UPPER LIMB SURGERY

Primary Investigator:	1) DR [name] (MBBS (Manipal), MMed Anaesthesiology (USM))
Co-investigators:	1) DR [name] (MBChB BAO (Queen's University of Belfast), PhD (Newcastle University))
	2) DR [name] (MD (UKM), MMed Anaesthesiology (USM))
	3) DR [name] (MD (USM), MMed Anaesthesiology (USM))
	4) DR [name] (MD (UIA), MSc Medical Statistics (USM))

UNIVERSITI SAINS MALAYSIA

Date of report: 30th NOVEMBER 2017

(Minor amendment: 20th MARCH 2018)

NCT ID: To be assigned

THE EFFICACY OF PARECOXIB 20MG AS AN ADJUNCT IN 0.75% ROPIVACAINE IN SUPRACLAVICULAR BRACHIAL PLEUXS BLOCK FOR UPPER LIMB SURGERY

ABSTRACT

Introduction

Brachial plexus block (BPB) is a critical method in providing anaesthesia for upper limb surgery. Parecoxib, a specific COX-2 inhibitor, has the potential as an adjunct for 0.75% ropivacaine in supraclavicular BP block setting.

Objectives

To investigate whether the efficacy of supraclavicular brachical block is enhanced by the addition of 20 mg parecoxib to 0.75% ropivacaine in patients undergoing upper limb surgery.

Methods

This is a double-blind, active-controlled, parallel group, prospective randomized clinical trial conducted between 20th June and 28th August 2017 involving eighty six (n=86) adults whose age were between 18 and 65 years old, with ASA grade I or II and undergoing various upper limb surgeries whose durations were between 1 and 4 hours. The subjects were block-randomized in 1:1 ratio into two groups; group 1 received adjunct IV parecoxib and 0.75% ropivacaine whilst group 2 received 0.75% ropivacaine alone. The primary end-points are the duration and onset of sensory and motor block and the proportions of complete motor and sensory block at 30 minutes following supraclavicular BP block. The significance of the differences in trial endpoints were statistically tested using Mann-Whitney and Chi-square tests.

Results

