Eighty six (n=86) subjects were randomised to either group and analysed. There were higher durations of sensory and motor blocks in the adjunct parecoxib + ropivacaine group compared to the ropivacaine-only groups (sensory block duration: 6.5 hours vs 5.0 hours, median difference = 1.5 hours, p value <0.001; motor block duration: 4.84 hours vs 3.86 hours, median difference = 0.97 hours, p value <0.001). No significant differences between the two intervention arms with respect to sensory (9 minutes vs 9 minutes, median difference = 0 minute, p value = 0.511) and motor blockades (17 minutes vs 18 minutes, median difference = 1 minute, p value = 0.832) onset. Besides, there no significant difference in terms of complete sensory and motor blockades at 30 minutes post supraclavicular block between parecoxib + ropivacaine and ropivacaine-only groups (sensory blockade at 30 minutes: 100% vs 97.7 %, p value = 1.000; motor blockade at 30 minute = 100% vs 97.7%, p value = 1.000). No adverse events were reported in both intervention arms and the trial was not ended prematurely.

Conclusion

Adjunct parecoxib significantly enhances the durations of sensory and motor blockades, but not their onset and complete sensory and motor block at 30 minutes following supraclavicular brachial plexus block.

(395 words)

SECTION ONE

INTRODUCTION

Brachial plexus block (BPB) has enjoyed ubiquitious popularity for upper limb surgeries (Raju and Coventry, 2013). It provides sufficient anaesthesia for surgical procedures involving upper limbs due to the propinquity of the brachial plexus' trunks and division when they pass the first rib (Gamo *et al.*, 2014).

There are a few common techniques for BPB and one of the most frequentlyutilised one is supraclavicular BPB (Raju and Coventry, 2013). It is not only an efficient mode of anaesthesia intraoperatively, but it is can also provide a quick-onset and dense anaesthesia for surgical procedures that involve the proximal mid-humerus down to the distal hand with excellent safety profile (Raju and Coventry, 2013; Gamo *et al.*, 2014). The supraclavicular block (SCB) is performed above the clavicle and aims at the level of the nerve trunks or division of brachial plexus (BP). Other frequently-employed alternatives include infraclavicular block, interscalene block and axillary BPB (Raju and Coventry, 2013).

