The level of significance was set at 0.05 and any p value that was less than 0.05 (p < 0.05) is considered significant. The analysis was performed in accordance to the intention-totreat (ITT) principle. A step-by-step summary of statistical methods employed for the analysis of this trial's data is given by figure 4.1 on the next page.

[figure not shown]

Figure 4.1: The step-by-step summary of the statistical methods used in this trial.

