5.3.3 The durations of sensory and motor block

There are significant differences in terms of the durations of sensory and motor block between the intervention arms and the differences are 1.5 hours and almost 1 hour, respectively (table 5.4). The evidence against null hypothesis can be considered very strong since the p values are less than 0.001 for both clinical outcomes. Hence, the null hypothesis of no significant difference can be safely rejected.

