The second limitation of our study is much more subtle. It is highly recommended that the future statistical analysis of a trial data should be done within the Bayesian framework, not solely within the frequentist setting. In this trial, the use of p values as the decision rule to determine whether a null hypothesis should be rejected or not may lead to incorrect conclusion since p value on itself is not the probability of a null (or studied) hypothesis is true (Wasserstein and Lazar, 2016). P value is actually just an assertion on the compatibility of our findings (or data) are with the hypothesis prespecified before the p value is obtained and assumed to be true (Wasserstein and Lazar, 2016). Besides, p value is also not a measure of effect size since a large p value does not mean that effect size is small and clinically negligible and a small p value represents a large and clinicallyrelevant effect size (Wasserstein and Lazar, 2016). Apart from that, p value is also not a measure whether a null hypothesis should be accepted or rejected since a small p value is not indicative of an evidence against null hypothesis or vice versa. This is because there are many other competing hypotheses that may be more compatible with the data than the tested null hypothesis (Wasserstein and Lazar, 2016). In fact, a borderline p value, for instance p equals 0.049, is just a weak against the null hypothesis and is usually lumped together with any p value that is less than 0.05 (Greenland et al., 2016). As a result of this statistical fallacy associated with the misinterpretation of p value, the number of positivebut-irreproducibe findings in trials will start to rise (Halsey et al., 2015).

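### Five of the six primary comparisons carry no confidence interval, yet non-significant onset results are read as no effect or as an attenuated effect

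*Combined protocol and SAP*

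**What the plan says.** The abstract states that the "primary end-points are the duration and onset of sensory and motor block and the proportions of complete motor and sensory block at 30 minutes", which makes six comparisons once sensory and motor are counted separately. It reports that "Eighty six (n=86) subjects were randomised to either group and analysed", 43 per arm.

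Section 4.13 plans a test for each outcome and adds that "The level of significance was set at 0.05". Neither its text nor Table 4.1 mentions a confidence interval or an effect measure. (Figure 4.1, the flow diagram of the methods, is not reproduced in the copy reviewed.)

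On the results:

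- **Onset.** Section 5.3.1 finds no significant difference and adds: "These are corroborated by the small median differences in both clinical outcomes when comparisons are made between these two groups".
- **Complete block at 30 minutes.** The abstract gives "sensory blockade at 30 minutes: 100% vs 97.7 %, p value = 1.000", with the same percentages and p value for motor block. Section 5.3.2 says "The odds ratio cannot even be computed because there are cells with 0 count". In Table 5.5 the column is headed odds ratio with 95% CI, and for both block outcomes it holds only a footnote mark with the same explanation.
- **Duration.** Section 5.3.3 says "The evidence against null hypothesis can be considered very strong since the p values are less than 0.001 for both clinical outcomes". Table 5.4 gives an interval for motor duration only.

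Section 6.1 then treats the onset result as showing that the effect of parecoxib is weaker with 0.75% ropivacaine than with the 0.25% used in the earlier axillary-block trial. Section 7 describes prolongation as conclusively shown and says that onset was not affected.

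**The concern.** A non-significant test says only that the data are compatible with no difference. Which other differences they are also compatible with is what an interval tells, and for four non-significant primary comparisons the report gives none. The step from not detected to not present, in Sections 6.1 and 7, therefore has no stated support.

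The attenuation claim asks for more still. It compares the effects in two trials, and a significant result in one beside a non-significant result in the other does not test that comparison. Section 2.4 gives durations from the earlier axillary-block trial but no onset figures, so the report does not show the size of the effect said to be attenuated.

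Two smaller matters follow. First, a difference of sample medians is not the quantity that a Mann-Whitney test addresses, and it is printed without precision. The 1.5 h for sensory duration equals three of the half-hourly assessment steps in Section 4.10.2. Second, the 30-minute outcomes are summarised by a p value that, as shown below, could not have been anything but 1.

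**Working it through.** **1. Which comparisons have an interval (Tables 5.4 and 5.5)**

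| Primary comparison | Parecoxib arm | Control arm | Difference printed | p | 95% CI |
|---|---|---|---|---|---|
| Sensory onset, median (IQR), min | 9.00 (2.25) | 9.00 (3.00) | 0 | 0.577 | none |
| Motor onset, median (IQR), min | 17.00 (5.00) | 18.00 (6.00) | -1 | 0.832 | none |
| Sensory duration, median (IQR), h | 6.50 (2.0) | 5.0 (2.00) | 1.50 | <0.001 | none |
| Motor duration, mean (SD), h | 4.84 (0.77) | 3.86 (0.60) | 0.97 | <0.001 | 0.68 to 1.27 |
| Complete sensory block, 30 min | 43/43 | 42/43 | none | 1.000 | none |
| Complete motor block, 30 min | 43/43 | 42/43 | none | 1.000 | none |

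Five of six have no interval. Four of those five are non-significant; the fifth, sensory duration, is significant.

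**2. The report's own figures reproduce**

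- Fisher, 43/43 v 42/43: there is one incomplete block in total, and under the null it falls in either arm with probability 43/86 = 0.5. The two possible tables are equally likely, so the two-sided p is 0.5 + 0.5 = 1.000. With one event and equal arms no other p value can occur.
- Welch, motor duration: SE = sqrt(0.77²/43 + 0.60²/43) = 0.149; t = 0.97/0.149 to 0.98/0.149 = 6.52 to 6.58 (stated 6.561); df 79.3 (stated 79.342).
- Mann-Whitney without tie correction, 43 v 43: mean U = 43 × 43/2 = 924.5; SD = sqrt(43 × 43 × 87/12) = 115.8. U = 861 gives z = -0.548, p = 0.583 (Table 5.4: 0.577). U = 900.5 gives z = -0.207, p = 0.836 (Table 5.4: 0.832). Both are consistent with a tie correction. The abstract prints 0.511 for sensory onset, which U = 861 does not support.

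**3. Risk difference at 30 minutes (same counts for sensory and motor)**

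- d = 43/43 - 42/43 = 1 - 0.9767 = +0.0233.
- Wilson 95% limits: 0.9180 to 1.0000 (parecoxib) and 0.8794 to 0.9959 (control).
- Newcombe lower limit: 0.0233 - sqrt((1 - 0.9180)² + (0.9959 - 0.9767)²) = 0.0233 - 0.0842 = -0.061.
- Newcombe upper limit: 0.0233 + sqrt((1 - 1)² + (0.9767 - 0.8794)²) = 0.0233 + 0.0973 = +0.121.

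The result is +2.3 percentage points (-6.1 to +12.1). The Agresti-Caffo method gives -5.2 to +9.6.

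**4. Odds ratio at 30 minutes**

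- Sample value: (43 × 1)/(0 × 42), which is infinite.
- Exact conditional limits: given one incomplete block and equal arms, the probability that it falls in the control arm is ψ/(1 + ψ), where ψ is the odds ratio for complete block. Setting this to 0.025 gives ψ = 0.025/0.975 = 0.026. There is no finite upper limit.
- With 0.5 added to each cell: (43.5 × 1.5)/(0.5 × 42.5) = 3.07 (95% CI 0.12 to 77.5).

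**5. Rough precision of the rank-tested outcomes (assumption: normal shape, SD = IQR/1.349)**

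- Mean-type half-width: 1.96 × sqrt((SD₁² + SD₂²)/43). Sensory onset, SDs 1.67 and 2.22 min: 0.8 min. Motor onset, SDs 3.71 and 4.45 min: 1.7 min. Sensory duration, SDs 1.48 and 1.48 h: 0.6 h.
- Median-type half-width (multiply by 1.2533): 1.0 min, 2.2 min and 0.8 h.

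Centred on the printed median differences, the median-type version gives -1.0 to +1.0 min, -3.2 to +1.2 min and +0.7 to +2.3 h. These show scale only. Section 5.2 says that all the continuous outcomes violated normality, and neither formula is the Hodges-Lehmann interval, which needs patient data.

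**The case against.** The other side has a good deal right.

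- **A reader might infer that Section 5.3.2 denies that any effect measure exists.** It does not. The sentence and the footnote speak only of the odds ratio, whose sample value does divide by zero. They are imprecise, because a finite lower limit exists. The real gap is that nothing replaces the blank cell.
- **A reader might infer that the null results cannot be interpreted.** That is too strong. Counts, medians and IQRs are printed, the risk difference is one subtraction, and the three rank-tested outcomes do carry a median difference. Section 5.3.1 cites those differences, and Section 5.3.3 states 1.5 hours and almost 1 hour before it mentions p values.
- **A reader might infer that Section 6.4 contradicts Section 5.3.3**, since it says that "a small p value is not indicative of an evidence against null hypothesis". The contrast is mainly one of wording. Section 6.4 argues that rival hypotheses may fit better, calls p = 0.049 weak, and warns that a p value is not an effect size. Grading evidence by p is compatible with that, and for motor duration the printed interval supports strong language.
- **The rough half-widths suggest that onset was measured fairly precisely.** They may even persuade a reader that a useful speed-up was excluded. The documents state no minimal important difference or equivalence margin, so that cannot be settled from them.

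What remains is that five intervals are absent, none was planned, and Sections 6.1 and 7 make positive statements from non-significant onset results.

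**Conclusion.** The point holds as a reporting and inference gap that should be corrected. Five of six primary comparisons lack a confidence interval. For 30-minute block the data are compatible with anything from about 6 points worse to 12 points better with parecoxib. For onset, the defensible statement is that no difference was detected. Neither absence of an effect nor attenuation relative to the earlier trial has been shown.

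Nothing here reverses a finding. Motor duration already has its interval, and under the rough approximation sensory duration stays clear of zero.

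The 30-minute figures rest only on the Table 5.5 counts and a two-sided 95% level (Section 4.13 does not state sidedness). The onset half-widths, about 0.8 to 1.0 min sensory and 1.7 to 2.2 min motor, rest on a normal-shape assumption that the report itself rejects. They should not be used to claim equivalence.

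**What to change.** - For sensory onset, motor onset and sensory duration, report the Hodges-Lehmann shift with its 95% CI, from the patient data held.
- For both 30-minute outcomes, report the risk difference with its Newcombe 95% CI: +2.3 points (-6.1 to +12.1).
- Replace the Section 5.3.2 sentence and the Table 5.5 footnote with a statement that the sample odds ratio is infinite and that the risk difference is given instead.
- In Section 7, and wherever the abstract and Section 6.1 repeat the claim, say that no difference in onset was detected, followed by the interval. Replace the attenuation claim in Section 6.1 in the same way, and do not claim equivalence.
- Add to Section 4.13 that each primary comparison is reported with an effect estimate and a 95% CI, marked as added after the analysis.

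The cost is a few lines of analysis on existing data and some text edits. The downside is that the null findings will read as less definite.

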5.3.3 The durations of sensory and motor block

There are significant differences in terms of the durations of sensory and motor block between the intervention arms and the differences are 1.5 hours and almost 1 hour, respectively (table 5.4). The evidence against null hypothesis can be considered very strong since the p values are less than 0.001 for both clinical outcomes. Hence, the null hypothesis of no significant difference can be safely rejected.

5.3.4 Other clinical parameters

For other clinical parameters, there is no single significant difference observed between the intervention groups. Hence, both groups exhibit fairly balanced effects of confounders. **Table 5.4:** The differences between the intervention arms in terms of sensory and motor block onset and durations and other clinical parameters (n=86).

Outcomes	Intervention arms		Median differences*	Mann-Whitney U statistics	p values
	Parecoxib + Ropivacaine Median (IQR)	Ropivacaine only Median (IQR)			
Sensory block onset (minutes)	9.00 (2.25)	9.00 (3.00)	0	861.00	0.577
Motor block onset (minutes)	17.00 (5.00)	18.00 (6.00)	-1	900.50	0.832
Sensory block luration (hours)	6.50 (2.0)	5.0 (2.00)	1.50	199.00	<0.001
Motor block luration (hours)	4.84 (0.77) ^a	3.86 (0.60) ^a	0.97 (0.68, 1.27) ^b	6.561 (79.342) ^c	<0.001
Age (years)	47.5 (26)	51.0 (21.0)	-3.5	838.00	0.455
Weight (kg)	60.0 (13.0)	60.0 (12.0)	0	809.50	0.399

*Parecoxib and Ropivacaine group minus Ropivacaine only group, ^aMean (SD), ^bMean difference (95% CI), ^cIndependent t-test for unequal variance (degree of freedom)

Table 5.5: The associations between the intervention arms in terms of the degrees of sensory and motor blockade at 30 minutes following supraclavicular brachial plexus block and other clinical parameters (n=86).

Outcomes	Intervention arms		Odds ratio (95% CI)	χ^2 statistics (df)	p values
	Parecoxib + Ropivacaine n (%)	Ropivacaine only n (%)			
Degree of sensory			_a	Not applicable	1.000
block					
Complete block	43 (100)	42 (97.7)			
Normal sensation	0 (0)	1 (2.3)			
Degree of motor block			_a	Not applicable	1.000
Flex / extend forerarm (grade I)	0 (0)	1 (2.3)			
No upper limb movement (grade IV)	43 (100)	42 (97.7)			
Gender			Not applicable	0.764 (1)	0.382
Female	16 (37.2)	20 (46.5)			
Male	27 (62.8)	23 (53.5)			
Ethnicity			Not applicable	Not applicable	1.000
Malay	42 (97.7)	41 (95.3)	TT TT	TT TT	
Chinese	1 (2.3)	1 (2.35)			
Others	$ \begin{array}{c} 1 \\ 0 \\ 0 \end{array} $ $ \begin{array}{c} 0 \\ 0 \end{array} $	1 (2.35) 1 (2.35)			

^aCannot be computed due to the presence of 0 cell count

ASA grades	7 (16.3)	6 (14.0)	Not applicable	0.091 (1)	0.763
I	36 (83.7)	37 (86.0)			
II					
Sites of surgery					
Forearm	14 (32.5)	8 (18.6)	Not applicable	Not applicable	0.102
Arm	21 (48.9)	31 (72.1)			
Hand	0 (0)	1 (2.3)			
Fingers	6 (14.0)	3 (7.0)			
Missing	2 (4.6)	0 (0)			

5.4 THE ADVERSE EVENTS ASSOCIATED WITH ROPIVACAINE AND / OR PARECOXIB

No subjects reported any significant and serious side effects associated with ropivacaine and parecoxib. The signs and symptoms of side effects that are commonly associated with ropivacaine administration such as CNS (seizures, peri-oral numbness, paraesthesia, dysaesthesia, tremor, dizziness) and cardiovascular toxicities (hypotension, bradycardia and arrythmias) were not reported by any study participant in both intervention groups. Besides, no significant side effects related to parecoxib administration (gastrointestinal bleeding, anaphylaxis reactions such as swelling, rash and breathing difficulties, jaundice, abnormal liver function tests etc.) were experienced by the study participants.

The trial was not stopped prematurely and lasted for the whole duration as planned.

SECTION SIX

DISCUSSION

6.1 THE ANTI-NOCICEPTIVE EFFECTS OF PARECOXIB IN SUPRACLAVICULAR BRACHIAL PLEXUS BLOCK

In this study, our primary finding is that synergistic combination of ropivacaine and parecoxib only prolonged the duration of sensory and motor blockades, not the onset of sensory and motor block. This proves that COX-2 inhibitors act centrally and that the spinal transmission of nociceptive signals is affected by constitutively-expressed COX-2 in the central nervous system. More generally, our results indicate that the antiinflammatory and antinociceptive effects of COX-2 inhibitors are not necessarily related since the dosage we used in this study was well below the dose required for antiinflammatory induction. However, the discrepancy between our findings and Liu et al. (2013) in terms of the onset of sensory and motor blockades can be attributed to the higher concentration of ropivacaine (0.75%) compared to one used by Liu et al. (2013) (0.25%) ropivacaine). As a result, Liu et a. (2013) reported a significant difference with regard to the onset of sensory and motor blockades between 0.25% ropivacaine + parecoxib recipients and those who received 0.25 % ropivacaine only. Therefore, our finding adds to the current knowledge by demonstrating the attenuation of 20 mg parecoxib's effect when it is used as an adjunct to a higher concentration of ropivacaine. Besides, we also generalised the findings and conclusion made by Liu et al. (2013), who only recruited subjects who were recipients of axillary brachial plexus blockade, by demonstrating that the benefits of adjunct parecoxib can also be extended to patients undergoing BPB via supraclavicular approach as well. We also sucessfully managed to control the confounding effects of preoperative (baseline) pain scores since both intervention groups exhibited identical mean visual rating scores (VRS). Consequently, the validity of our findings is more bona fide than the ones asserted by Liu *et al.* (2013).

The prolongation of sensory and motor blockades upon the addition of 20 mg parecoxib to ropivacaine is still not well-understood. There are several explanations that can be put forward to expound these findings. Firstly, the inhibition of COX-2's action will result in a decrease in the production of prostacyclin (a potent vasodilator), whilst conserving the synthesis of the vasoconstrictive thromboxane A₂. Consequently, parecoxib prolonged the duration of anaesthetic action in a similar fashion like the vasoconstrictive effect produced by adjunct epinephrine mixed with LA agents for infiltrative anaesthesia (Newton *et al.*, 2004). Next, the action of ropivacaine on sodium channels might be altered by the addition of parecoxib. Butterworth IV and Strichartz (1990) had hypothesized that there were a multitude of LA's mechanisms of actions for spinal and epidural analgesia and one of them was via the reduction of prostacylin and prostaglandin production, resulting in a modulated effect of LA on sodium channel bloackade. Thirdly, the inhibitory effect of parecoxib on COX-2 may also decrease the production of prostanoid centrally, hence reducing the effects of peripheral inflammation and the ensuant mechanical hypersensitivity (Samad *et al.*, 2001).

NSAIDSs have long been considered to have effects on the CNS via COX inhibition, as numerous experimental models over the past 15 years have established. The findings that both COX isoforms are expressed in the CNS and the fact that central nociceptive transmission and pain hypersensitivity secondary to mechanical inflammation are modulated by COX-2 following peripheral inflammation lend further support to this notion (Choi *et al.*, 2009; Vardeh *et al.*, 2009). These observations question the classical perception that NSAIDs's antinociceptive effect was solely attributed to preventing the sensitization of nociceptor (Sinatra 2002). Nevertheless, the peripheral and

central modes of NSAID actions should not be regarded as mutually independent but as complementary and possibly synergistic. Furthermore, the fact that COX-2 is also constitutively expressed in the CNS hints towards its role in modulating pain induced by even the normal physiological processes (Burian and Geisslinger, 2005; Martin *et al.*, 2007).

Nevertheless, the arguments about the roles of COX-2 enzymes in central pain modulation in both normal physiological and pathological settings were far from conclusive since they chiefly relied upon the findings obtained from animal models, not from experiments or trials involving human subjects. Thus far, the central effects of COX-2-specific inhibitors in humans was solely investigated in the setting of primary and secondary hyperalgesia caused by sunburn injury due to exposure to an ultraviolet-B (UVB) radiation, the application of electrical stimulation transdermally and skin sensitization via capsaicin exposure (Sycha *et al.*, 2005; Koppert *et al.*, 2004; Burns *et al.*, 2006). However, the generalisability of the findings obtained from these experimental models is still restrictive due to their ancillary methods used to evaluate the intervention's central analgesic effects. Moreover, the findings were also heavily biased since the experimental results obtained were contingent upon the types of experimental pain model used by the researchers. This may hence cause the negative results reported by Burns and coworkers (2006).

The primary issue that prevents the researchers from gaining a concrete evidence and thus conclusively confirming the authenticity of COX-2-specific inhibitor's central antihyperalgesic effect is that in the majority of pain states induced by inflammatory causes, a mixture of peripheral and central sensitization materalises. As a result, it is indeed laborious to distinguish the peripheral from spinal components of the antihyperalgesic effects attributed to COX-2-selective inhibitor. The effect of antidromic

70

electrical stimulation on peripheral sensitization had been negated by the prior work of Schmeltz *et al.* (1996). In fact, Klede *et al.* (2003) had assuringly established, using an anaesthetic strip experiment, that in the setting of electrically-induced mechanical hyperalgesia, the origin of such hyperalgesic state is centrally located, not peripherally located. The unvarying pain scores obtained prior to and following the exposure to the electrical stimuli and the absence of clinically and statistically meaningful decrease in axon reflex erythema, which has a peripheral hyperalgesic component, further corroborate the belief that COX inhibitors' peripheral effects did not result in evident antihyperalgesic effect (Koppert *et al.*, 2004).

The central release of prostaglandins which results in the creation of hyperalgesic state is a fact that has been agreed upon by the scientific community (Vanegas and Schaible, 2001). Nevertheless, the involvement of disparate molecular and cellular mechanisms in the production of the central hyperalgesic effects induced by prostaglandins is still yet to be wholly comprehended. Baba *et al.* (2001) demonstrated that PGE₂ has the ability to precisely depolarize the neurons located at spinal dorsal horns through the EP₂ receptors. Furthermore, the blockade of glycinergic neural signal transmission of the inhibitory neurons by PGE₂ through blocking the glycine receptor that posesses α 3 subunit could also be one of the critical mechanisms of inflammatory hyperalgesia (Zeilhofer, 2005). Hence, it is highly likely that the addition of parecoxib may remove the blockade to the α 3 glycine receptor and hence prolonging the duration of sensory and motor blockade by improving the glycinergic neural signal transmission.

